6.7 Medical Devices

Non-investigational medical devices may be used in the conduct of this study as part of standard care.

Non-Amgen non-investigational medical devices (eg, syringes, sterile needles, alcohol prep pads), that are commercially available are not usually provided or reimbursed by Amgen (except, for example, if required by local regulation). The investigator will be responsible for obtaining supplies of these devices.

6.8 Product Complaints

A product complaint is any written, electronic or oral communication that alleges deficiencies related to the identity, quality, durability, reliability, safety, effectiveness, or performance of any investigational or non-investigational product(s) or device(s) after it is released for distribution to market or clinic by either Amgen or by distributors and partners for whom Amgen manufactures the material.

Any product complaint(s) associated with an investigational product(s) or non-investigational product(s) or device(s) supplied by Amgen are to be reported according to the instructions provided in the IPIM.

6.9 Excluded Treatments and/or Procedures During Study Period

Subjects must not use any of the following therapies during screening or treatment period (including retreatment for post-CR relapse) of this trial:

- investigational agents (other than pembrolizumab and talimogene laherparepvec) or procedures
- warfarin. Other anticoagulants (ie. low molecular weight heparins, non-steroidal anti-inflammatory drugs) that do not prolong the PT/INR may be administered after investigator discussion with the sponsor and as long as there is adherence to institutional guidelines requiring their withholding for interventional radiology procedures.
- concurrent experimental or approved anti-tumor therapies or biological therapy other than study drug and radiation therapy required for palliation (as noted in Section 6.5)

Note: Radiation therapy to a symptomatic solitary lesion or to the brain may be considered on an exceptional case by case basis after consultation with Sponsor. The subject must have clear measurable disease outside the radiated field. Administration of palliative radiation therapy will be considered clinical progression for the purposes of determining PFS.

- immunotherapy not specified in this protocol
- chemotherapy not specified in this protocol

- chronic oral or systemic steroid medication use at a dose of >10 mg/day of prednisone (1.5 mg/day dexamethasone) or equivalent (with the exception of treatment for adverse events [see Section 6.2.1.2] and CNS metastases [see Section 6.5]). Steroids with low systemic absorption [eg, triamcinolone hexacetonide] injected into a joint space, and intermittent use of steroid inhalers or topical steroid is allowed).
- antiherpetic drugs, except those topically administered
- live vaccines within 30 days prior to the first dose of trial treatment and while participating in the trial. Examples of live vaccines include, but are not limited to, the following: measles, mumps, rubella, chicken pox, yellow fever, rabies, Bacillus Calmette-Guerin (BCG), and typhoid (oral) vaccine. Seasonal influenza vaccines for injection are generally killed virus vaccines and are allowed. However, intranasal influenza vaccines (eg, Flu - Mist[®]) are live attenuated vaccines, and are not allowed.
- any surgery for cancer (other than the exceptions noted in Section 6.6)
- Subjects must not schedule any elective non-cancer-related surgeries during the treatment period and for at least 30 days after the last administration of study drug. If a subject undergoes any unexpected surgery during the course of the study, study treatment must be withheld and the investigator or designee should notify the sponsor medical monitor as soon as possible. A subject may be allowed to resume study drug if both the investigator and sponsor medical monitor agree to restart study therapy.
- Subjects who, in the assessment by the investigator, require the use of any of the aforementioned treatments for clinical management should be removed from the trial. Subjects may receive other medications that the investigator deems to be medically necessary.

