Dosing should be permanently discontinued if, in the opinion of the investigator, the subject develops clinical evidence of any serious herpes infection (such as HSV hepatitis, encephalitis, or disseminated infection). Systemic anti-herpetic drugs (eg, acyclovir, valacyclovir, or famciclovir) should only be reserved for suspected cases of severe herpetic infection as outlined in the Guidelines for Suspected Serious Herpetic Infections document, but topically administered anti-herpetic drugs may be administered for limited suspected herpetic skin lesions after they are swabbed and tested for talimogene laherparepvec using qPCR.

For Part 1 Group A Cohorts 1-6, Part 1 Group B Cohorts 5 and 6a, and Part 2 Arms I-VI, in subjects with history of HBV and HCV, viral load should be rechecked when ALT or AST are elevated more than twice their baseline value. If reactivation of HBV or HCV is confirmed, discontinuation of talimogene laherparepvec and starting hepatitis antiviral medication should be considered after consultation with the sponsor medical monitor.

For Part 1 Group B Cohort 6b and Part 2 Group B Arm VI subjects with well-controlled viral hepatitis, please see [Table 15](#). Subjects who discontinue talimogene laherparepvec are to continue to return for all other study procedures and

measurements including the 30-day safety follow-up visit (ie, until approximately 30 [+ 7] days after the last dose of study drug) and long term survival follow-up.

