7.2.3.2 Survival Follow-up

All subjects who permanently discontinue study drug for any reason other than withdrawal of full consent will be contacted by clinic visit or telephone to assess survival, talimogene laherparepvec-related adverse events, and initiation of additional anti-tumor treatment. For subjects in the combination treatment cohort, the long-term follow-up starts after the discontinuation of whichever study drug is discontinued last.

For Part 1, contact for all subjects will be attempted approximately every 12 weeks (± 28 days) following the safety follow-up visit until death, subject withdrawal, or up to approximately 24 months after the date of the last subject enrolled in Part 1. Subjects in Cohort 5 and 6 will be followed approximately 24 months after the last subject enrolled in their cohort in Part 1, or approximately 24 months after the last subject enrolled with their tumor type in Part 2, whichever is later.

For Part 2, contact for all subjects will be attempted approximately every 12 weeks (± 28 days) following the safety follow-up visit until death, subject withdrawal, or up to approximately 24 months after the date of the last subject enrolled in that tumor cohort.

[figure not shown]
Radiographic Tumor Assessment: Every effort should be made to complete radiographic assessments approximately every 12 (+1) weeks during the long-term follow-up until documentation of PD per modified irRC-RECIST ([Appendix D](#)), start of new anticancer treatment, death, or end of study, whichever occurs first, for subjects discontinuing treatment for any reason other than PD. In Part 2, clinical tumor assessment, if applicable, should be performed and documented at these timepoints as well. Response (CR, or PR) or disease progression to be confirmed by second consecutive radiographic assessments no less than 4 weeks from the date of the first documented response or disease progression. Note: Confirmation of disease progression is required only in the absence of rapid clinical deterioration (ie, rapid

[figure not shown]
decline in performance status) symptomatic disease requiring rapid initiation of alternative systemic anti-cancer therapy.

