8. WITHDRAWAL FROM TREATMENT, PROCEDURES, AND STUDY

8.1 Subjects' Decision to Withdraw

Subjects have the right to withdraw from the study at any time and for any reason without prejudice to their future medical care by the physician or at the institution.

Subjects (or a legally acceptable representative) can decline to continue receiving investigational product and/or other protocol-required therapies or procedures at any time during the study but continue participation in the study. If this occurs, the investigator is to discuss with the subject the appropriate processes for discontinuation from investigational product or other protocol-required therapies and must discuss with the subject the options for continuation of the Schedule of Assessments (Table 8 through Table 13) including different options for follow-up (eg, in person, by phone/email, through family/friends, in correspondence/communication with other treating physicians, the review of medical records) and collection of data, including endpoints and adverse events. Subjects that have discontinued investigational product and/or protocol required therapies or procedures should not be automatically removed from the study. Whenever safe and feasible, it is imperative that subjects remain on study to undergo safety surveillance and/or collection of outcome data. The investigator must document the change to the Schedule of Assessments (Table 8 through Table 13) and the level of follow-up that is agreed to by the subject (eg, in person, by telephone/mail, through family/friends, in correspondence/communication with other physicians, from review of the medical records).

For subjects who discontinue investigational product without documented PD and have not initiated a new anticancer therapy, every effort should be made to continue monitoring tumor response status by clinical and radiographic tumor assessments as described in [Table 8](#) through [Table 13](#).

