Those subjects who discontinue investigational product should continue into long-term follow-up. Subjects in Part 1 will be followed for survival, talimogene laherparepvec related adverse events, and subsequent anticancer therapies every 12 weeks (± 28 days) for approximately 24 months after the last subject is enrolled in Part 1. Subjects in Part 2 will be followed for survival, talimogene laherparepvec related adverse events, pembrolizumab related adverse events (if applicable), and subsequent anticancer therapies every 12 weeks (± 28 days) for approximately 24 months after the last subject is enrolled per tumor type cohort.

Withdrawal of consent for a study means that the subject does not wish to receive further protocol-required therapies or procedures, and the subject does not wish to or is unable to continue further study participation. Subject data up to withdrawal of consent will be included in the analysis of the study, and where permitted, publically available data can be included after withdrawal of consent. The investigator is to discuss with the subject appropriate procedures for withdrawal from the study.

8.2 Investigator or Sponsor Decision to Withdraw or Terminate Subjects' Participation Prior to Study Completion

The investigator and/or sponsor can decide to withdraw a subject(s) from investigational product and/or other protocol-required therapies, protocol procedures, or the study as a whole at any time prior to study completion.

Subjects may be eligible for continued treatment with Amgen investigational product(s) and/or other protocol-required therapies by a separate protocol or as provided for by the local country's regulatory mechanism, based on parameters consistent with [Section 12.1](#).

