8.3.2 Reasons for Removal From Study

Reasons for removal of a subject from the study are:

- decision by sponsor
- withdrawal of consent from study
- death
- lost to follow-up

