Subjects should be informed that taking pembrolizumab may involve unknown risks to the fetus (unborn baby) if pregnancy were to occur during the study. In order to participate in the study, men and women of reproductive potential must adhere to the contraception requirements (See Section 4.1.2, exclusion criteria 224, 225, and 226) from the day of pembrolizumab initiation (or 14 days prior to the initiation of pembrolizumab for oral contraception) throughout the study period up to 4 months (120 days) after the last dose of pembrolizumab. If there is any question that a subject of reproductive potential will not reliably comply with the requirements for contraception, that subject should not be enrolled into the study.

Use of Pembrolizumab in Pregnancy

If a subject inadvertently becomes pregnant while on treatment with systemic pembrolizumab, the subject will immediately be removed from the study. The outcome of the pregnancy will be reported to the sponsor and followed as described in Section 9.3 (Pregnancy and Lactation Reporting). If a male subject impregnates his female partner, the investigator must be informed immediately and the pregnancy reported to the sponsor and followed as described in Section 9.3 (Pregnancy and Lactation Reporting).

Use of Pembrolizumab in Nursing Women

It is unknown whether pembrolizumab is excreted in human milk. Since many drugs are excreted in human milk, and because of the potential for serious adverse reactions in the nursing infant, female subjects who are breast-feeding are not eligible for enrollment in this study.

Amendment 6

Protocol Title: A Phase 1b/2, Multicenter, Open-label, Basket Trial to Evaluate the Safety of Talimogene Laherparepvec Injected into Liver Tumors Alone and in Combination With Systemic Pembrolizumab in Phase 1b and to Evaluate the Efficacy and Safety of Intratumoral Talimogene Laherparepvec in Combination With Systemic Pembrolizumab to Treat Subjects With Advanced Solid Tumors in Phase 2 (MASTERKEY-318)

Amgen Protocol Number (Talimogene Laherparepvec 20140318)

EudraCT number: 2014-005386-67

NCT number: NCT02509507

Amendment Date: 26 October 2021

Rationale:

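### Section 6.9 removes subjects who need a prohibited treatment from the trial, in conflict with the sections that keep them in follow-up; applied literally it would cut short survival and late safety data

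*Protocol*

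**What the plan says.** Section 6.9 opens its list with "Subjects must not use any of the following therapies during screening or treatment period". The list covers other investigational agents, warfarin, concurrent anti-tumor therapy, immunotherapy and chemotherapy outside the protocol, chronic steroids above a threshold, non-topical antiherpetics, live vaccines and cancer surgery. Some items carry exceptions: steroids for adverse events or CNS metastases, palliative radiation, and the surgery allowed in Section 6.6. The section closes by saying that subjects who, in the investigator's assessment, "require the use of any of the aforementioned treatments for clinical management should be removed from the trial". It makes no provision for follow-up after removal.

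Elsewhere the protocol separates leaving treatment from leaving the study:

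- Section 8.1 says that subjects who have stopped product or procedures "should not be automatically removed from the study", and adds: "Those subjects who discontinue investigational product should continue into long-term follow-up".
- Section 7.2.3.2 begins: "All subjects who permanently discontinue study drug for any reason other than withdrawal of full consent will be contacted by clinic visit or telephone". The contacts cover survival, related adverse events and new anti-tumor treatment.
- Section 8.3.1 lists need for alternative therapy, and pregnancy, as reasons for removal from treatment.
- Section 8.3.2 introduces its list with "Reasons for removal of a subject from the study are" and gives four: sponsor decision, withdrawal of consent, death and loss to follow-up.

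Appendix I, on a subject who becomes pregnant while on pembrolizumab, says "the subject will immediately be removed from the study".

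**The concern.** A site with a subject on treatment who needs another therapy can find an instruction to end that subject's participation in 6.9 and an instruction to continue it in 7.2.3.2 and 8.1. Both triggers are foreseeable. Section 3.5.1 names deterioration requiring alternative systemic therapy as a reason to stop talimogene laherparepvec. Section 6.2.1.2 says systemic antiherpetics "should only be reserved for suspected cases of severe herpetic infection", so their use is planned for, yet they are on the 6.9 list.

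Two things are at stake.

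- **Overall survival** is a secondary endpoint in both parts. The SAP (Section 5) censors a subject without a confirmed death at the date last known alive, and SAP Table 9-2 plans no sensitivity analysis. Censoring because a subject needs new anticancer therapy is unlikely to be independent of the risk of death. Kaplan-Meier assumes that it is.
- **Late safety data** would be lost: the safety visit, serious adverse event collection and the 12-weekly contacts. For a subject given a systemic antiherpetic, this would happen just when a possibly virus-related event needs follow-up.

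**Working it through.** The point is mainly textual; the plan gives no figure to reproduce.

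**Step 1: the instructions side by side**

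| Situation | Section 6.9 | Other sections |
|---|---|---|
| Needs a new anticancer agent while on treatment | Leaves the trial | 6.2.1.2: talimogene laherparepvec treatment is discontinued. 8.3.1: removal from treatment. 7.2.3.2: contacted about survival and new therapy |
| Given a systemic antiherpetic for suspected severe herpetic infection | Leaves the trial | 6.2.1.2: use foreseen; subjects off talimogene laherparepvec keep the other study procedures, the 30-day safety visit and survival follow-up |
| Needs any other listed item | Leaves the trial | 8.3.2: not one of the four reasons for leaving the study |
| Pregnancy | Not covered (Appendix I: leaves the study) | 8.3.1: removal from treatment. 9.3: outcome followed |

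Because the protocol separates treatment from study in Section 8, a site cannot safely read the trial in 6.9 as meaning only treatment.

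**Step 2: which endpoints are exposed when the trigger is new anticancer therapy**

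- ORR and BOR: the SAP (Section 5) excludes assessments after subsequent anticancer therapy starts and counts subjects without a confirmed response by then as non-responders. Removal at that point changes little.
- DOR: ongoing responses are censored at the last evaluable assessment before that therapy, and Section 7.2.3.2 ends imaging when it starts. Again little change.
- Serious adverse events: Section 9.2.3 already shortens the required window from 90 (+7) to 30 (+7) days for these subjects. What would be lost is that shorter window and the later contacts.
- OS: fully exposed, since deaths after removal would not be seen through study contact.

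For triggers that are not anticancer therapy, such as a systemic antiherpetic, literal removal could also cut response and PFS assessments short.

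**Step 3: direction of the OS effect, under assumptions**

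None of these inputs comes from the documents: median time to progression 4 months (rate λ = ln 2 / 4 = 0.173 per month); monthly death hazard d0 = 0.02 before progression and d1 = 0.09 after it; a fraction f of progressing subjects removed and censored 0.5 month after progression.

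With A(t) = exp(−(λ + d0)t) not progressed and B(t) = λ[exp(−d1·t) − exp(−(λ + d0)t)] / (λ + d0 − d1) progressed and alive, the progressed subjects still observed (for t > 0.5; before that C = B) are C(t) = B(t) − f·B(t − 0.5)·exp(−0.5·d1). The Kaplan-Meier curve follows the hazard (d0·A + d1·C) / (A + C).

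| f | Median OS (months) | 12-month OS |
|---|---|---|
| 0 (true) | 12.1 | 50% |
| 10% | 12.3 | 51% |
| 30% | 12.8 | 53% |
| 60% | 14.1 | 58% |
| 80% | 16.0 | 63% |

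With d1 = 0.12, the true median of 10.3 months reads 11.1 at f = 30% and 14.4 at f = 80%.

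For scale, the approximate 95% margin on a 50% 12-month survival rate is 1.96·√(0.25/n): ±31 points for n = 10 and ±21 points for n = 21.

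**The case against.** The strongest answer is that 6.9 is one loose sentence against several operative sections, and that a sensible site would follow the latter. Nothing in the documents shows that any subject has been removed on this ground. That stands, so the effect is conditional on a site giving 6.9 precedence.

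Other points also stand in part:

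- The 6.9 list applies to screening and treatment. Confirmed progression already ends talimogene laherparepvec under 6.2.1.2, and therapy given after treatment has ended is ordinary follow-up information. The exposed group is those judged to need a listed treatment while still on study treatment.
- Section 8.2 lets the investigator or sponsor withdraw a subject from the whole study, so the four reasons in 8.3.2 are not the only route out. But 8.2 is discretionary and does not call for removal here.
- Section 12.4 allows public-record searches for survival status where permitted. This recovers some deaths, but not adverse events or subsequent therapy.
- Section 9.2.3.1 follows reported adverse events to resolution or stabilization, which argues against dropping a subject with a herpetic infection.
- OS is descriptive and single-arm. Section 10.4 reserves formal analysis for the Part 2 primary endpoints. With arms of 10 to 21 subjects, the modest shifts in the table are well inside sampling error.

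A reader might go further and infer that follow-up does stop for all these subjects, that the primary response rate is biased, that a 90-day event window is lost after new anticancer therapy, or that pregnancy outcomes go unrecorded. The documents do not support these. Most sections continue follow-up; the response rules already cut off at new therapy; the window is already 30 (+7) days; and Appendix I itself refers the pregnancy outcome to Section 9.3.

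**Conclusion.** The contradiction is real. Section 6.9 ends trial participation for a reason that 8.3.1 assigns to treatment and 8.3.2 omits, while 6.2.1.2, 7.2.3.2 and 8.1 keep the same subjects under observation. If 6.9 is applied literally, survival and late safety follow-up would be lost; where the trigger is new anticancer therapy, OS would probably be censored informatively and look too favourable.

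The direction rests on one assumption, that subjects needing new therapy die sooner than those remaining under observation. The size cannot be derived, because the documents give neither the expected number of such subjects nor their hazards. The table is illustrative, and its larger rows need most progressing subjects to be removed against 7.2.3.2 and 8.1. In Appendix I only the study-versus-treatment wording conflicts with 8.3.1.

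Severity is moderate. The endpoint is secondary and descriptive. Enrollment has stopped (Section 4), but survival follow-up is planned to about 24 months after the last enrollment (Section 3.5.1), and missed contacts are hard to recover.

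**What to change.** - Reconcile 6.9 with 6.2.1.2, 7.2.3, 8.1, 8.3.1 and 8.3.2. State that needing a listed treatment is not by itself a reason for removal from the study, and that the subject stays in the safety visit, serious adverse event collection, and survival and subsequent-therapy follow-up already planned, unless an 8.3.2 reason applies. Leave what happens to study treatment for each listed item to the existing sections.
- Reconcile the Appendix I wording with 8.3.1 in the same way. Its reference to Section 9.3 needs no change.
- Ask sites to identify anyone removed solely because of 6.9 and, with consent, resume survival follow-up. Report the number of such subjects beside the OS estimates.

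The cost is a short amendment and a site letter. Section 12.1 requires ethics committee approval, and Section 3.2 expects about 50 sites, so there is some administrative work and possibly a few re-contacts. No new visits or assessments are needed.
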